## 1. Synopsis

- Design: Interventional, randomized, parallel-group, three-arm educational trial.
- Arms: (A) Digital interactive peer support; (B) Face-to-face peer support; (C) Standard training (control).
- Primary Endpoint: Objective Structured Clinical Examination (OSCE) total score immediately post-intervention (points; higher is better).
- Secondary Endpoints: Reflection skills scale total score immediately post-intervention; Retention assessed by a follow-up OSCE at a predefined interval (e.g., 8–12 weeks).
- Setting: Clinical Skills Laboratory within a Faculty of Medicine in Türkiye.
- Population: Adult medical students meeting eligibility criteria.
- Allocation: Approximately 1:1:1; no masking.
- Estimated/Actual Enrollment: About 100 participants (retrospective registration of a completed trial).

## 2. Background and Rationale

Peer support is widely used in health professions education to promote practice, feedback, and reflection. Digital interactive platforms may expand access and flexibility compared with traditional face-to-face sessions. This study evaluates whether structured digital peer support is non-inferior or superior to face-to-face peer support, and whether either approach improves clinical skill performance compared with standard training.

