## 3. Objectives

**Primary Objective.** Compare post-intervention clinical skill performance between arms using OSCE total scores.

**Secondary Objectives.** Compare reflection skills between arms immediately post-intervention; evaluate retention of clinical skills at follow-up OSCE; explore relationships between outcomes and exposure to peer support.

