# Statistical Analysis Plan (SAP)

This SAP prespecifies analysis populations, endpoints, statistical tests, missing data handling, and multiplicity control. Analyses will be conducted using a two-sided significance level of 0.05.

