## 14. Primary Endpoint Analysis

Between-arm comparison of immediate post-intervention OSCE total scores: if assumptions are met, one-way ANOVA; otherwise, Kruskal-Wallis test. If the omnibus test is significant, perform pairwise comparisons with multiplicity adjustment (e.g., Bonferroni or Holm).

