## 15. Secondary Endpoint Analyses

Reflection skills total score will be analyzed analogously to the primary endpoint. Retention of skills will be evaluated by comparing follow-up OSCE total scores between arms at the predefined time point using ANOVA or Kruskal-Wallis as appropriate.

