## 18. Multiplicity

For multiple pairwise comparisons following a significant omnibus test, p-values will be adjusted (e.g., Bonferroni/Holm) to control the family-wise error rate.

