## 20. Administrative Information

Sponsor/Institution: [University / Faculty of Medicine]. Study officials and contacts are listed in the trial registry record. This public document does not include participant names or personally identifiable information.

Any deviations from this plan will be documented in the results submission. This version supersedes prior versions as of the Document Date.

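### The Background poses a non-inferiority question for digital versus face-to-face support, but the SAP contains only gated difference tests, with no margin or interval

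*Combined protocol and SAP*

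**What the plan says.** The Background (Section 2) sets the question: "This study evaluates whether structured digital peer support is non-inferior or superior to face-to-face peer support". The Primary Objective (Section 3) is more general and names no direction or hypothesis: "Compare post-intervention clinical skill performance between arms using OSCE total scores".

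The SAP follows the general wording. Its opening paragraph fixes the level: "Analyses will be conducted using a two-sided significance level of 0.05". Section 14 specifies a one-way ANOVA or a Kruskal-Wallis test across the three arms, and then: "If the omnibus test is significant, perform pairwise comparisons with multiplicity adjustment (e.g., Bonferroni or Holm". Section 18 repeats the gate: "For multiple pairwise comparisons following a significant omnibus test, p-values will be adjusted (e.g., Bonferroni/Holm) to control the family-wise error rate".

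Section 15 carries the scheme to one secondary endpoint: "Reflection skills total score will be analyzed analogously to the primary endpoint". For the follow-up OSCE it names only the omnibus tests, so any pairwise step there would come from Section 18.

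The Synopsis gives about 100 participants allocated roughly equally to three arms, and describes the registration as "retrospective registration of a completed trial". Section 20 adds: "Any deviations from this plan will be documented in the results submission".

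**The concern.** A non-inferiority claim needs a margin and an interval (or an equivalent one-sided test) to set against it. A difference test that fails to reject gives neither. Under this plan, if the omnibus test is not significant, digital and face-to-face are not compared at all. If it is significant but the pairwise test is not, the result is only an adjusted p-value above 0.05.

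The superiority half of the Section 2 question is covered, and a significant result favouring digital would also establish non-inferiority for any positive margin. No other result can support non-inferiority. Nor does any section say how a non-significant comparison may be described. A reader who takes Section 2 as the aim could read a null result as showing that digital is as good as face-to-face, when the trial may have missed a real deficit.

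**Working it through.** **1. Text check.** Sections 12 to 18 were searched for a margin, a non-inferiority hypothesis, a one-sided test, a confidence interval or a decision rule. There is none. Section 13 plans means, SDs, medians and ranges only. Sections 16 and 17 (exploratory covariate models, missing data) do not fill the gap. A per-protocol set is defined but assigned to no analysis. There is no sample-size calculation to reproduce.

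**2. Inputs.** From the Synopsis: about 100/3 ≈ 33 per arm. From the SAP: two-sided 0.05, ANOVA gate, Bonferroni or Holm. Assumed, because the documents give no SD, important difference or margin: normal scores, common SD, effects in SD units over a range.

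**3. Precision of digital minus face-to-face.** With 3 × 33 − 3 = 96 degrees of freedom:
- SE = √(2/33) = 0.246 SD
- unadjusted 95% half-width = t(0.975; 96) × SE = 0.489 SD
- Bonferroni half-width = t(1 − 0.05/6; 96) × SE = 0.600 SD

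**4. Simulation of the plan as written.** 200,000 trials per scenario: ANOVA F at 0.05, then pooled-SD pairwise t-tests. Paired figures are Bonferroni/Holm.

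Digital and face-to-face truly equal:

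| Both peer arms above control by | Omnibus not significant | Digital declared better |
|---|---|---|
| 0 | – | 0.80% / 0.87% |
| 0.3 SD | 78.2% | – |
| 0.5 SD | 46.9% | 0.83% / 1.27% |
| 0.8 SD | 7.8% | 0.83% / 1.85% |

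Dashes mark quantities not tabulated in these runs. A separate 40,000-trial run with all arms equal left the gate closed in 95% of trials, as expected at a 5% level.

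Digital truly worse than face-to-face, no difference declared between them:

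| Digital worse by | Control equal to digital | Control 0.5 SD below digital |
|---|---|---|
| 0.3 SD | 88.5% / 87.7% | 88.4% / 83.5% |
| 0.5 SD | 65.5% / 63.1% | 65.3% / 55.3% |
| 0.8 SD | 21.0% / 18.0% | 20.9% / 12.8% |

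**5. How much of this is sample size.** With control equal to digital, the unadjusted 95% CI excludes zero while the gated adjusted test is not significant in 11.1%/10.3% (0.3 SD), 17.5%/15.2% (0.5 SD) and 10.6%/7.6% (0.8 SD) of trials. Subtracting the Bonferroni figures, an ungated unadjusted interval would still include zero in 88.5 − 11.1 = 77.4%, 65.5 − 17.5 = 48.0% and 21.0 − 10.6 = 10.4%.

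**6. For reference.** A non-inferiority test at one-sided 0.025 with true difference zero and 33 per arm would have power of 12%, 23%, 52% and 90% at illustrative margins of 0.2, 0.3, 0.5 and 0.8 SD.

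**The case against.** The strongest reply is that the non-inferiority wording appears once, in the rationale. The objectives, endpoints, design and SAP agree with each other on a plain comparison of arms. No section says a null result will be called non-inferior, so the harm is a risk and not a planned error. That stands, and it is why the point does not touch the primary analysis. But the sentence is written as what the study evaluates, and a reader may fairly take it as an aim.

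A second reply is that a significant loss for digital is also informative. It is: with control equal to digital, it would be declared in about 35%/37% of trials at 0.5 SD worse and 79%/82% at 0.8 SD. It shows digital to be worse, but without a margin it does not settle whether the shortfall is acceptable.

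Third, most of the missed differences reflect 33 per arm and not the gate, as step 5 shows. This also stands. An interval makes the uncertainty visible but does not shrink it, and step 6 shows that even a proper non-inferiority test would be weak unless the margin were large.

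Finally, if the Section 13 means and SDs are reported by arm, readers could build an interval themselves. The section does not say they will be, and readers should not have to.

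**Conclusion.** The concern holds. Followed exactly, the plan cannot support non-inferiority unless digital wins significantly, which happens in 0.8% to 1.9% of trials when the two formats are equal. A null result is the usual finding under true equality and also when digital is 0.3 to 0.5 SD worse (about 55% to 89% of trials across the scenarios and adjustments examined), so it cannot tell these apart. That the plan cannot support the claim follows from the text alone. The percentages rest on 33 per arm, normal scores, a common SD and assumed effects in SD units. The point should be fixed, but it does not undermine the planned test of the formal primary objective.

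**What to change.** - **Section 14:** report the digital minus face-to-face difference in OSCE total score with a two-sided 95% CI whatever the omnibus result. Label it as unadjusted for multiplicity, or give the Bonferroni-adjusted interval beside it. If the Kruskal-Wallis branch is taken, still give the mean difference or a Hodges-Lehmann shift with its CI.
- **Section 14, wording rule:** state that a non-significant digital versus face-to-face result will not be described as non-inferior, equivalent or comparable.
- **Section 2:** because the trial is complete, do not remove the aim silently. Make a dated, disclosed amendment saying that non-inferiority was not formally tested, and list it with the deviations that Section 20 undertakes to document.
- **Margin:** only if one was documented before outcome data were seen, state it and judge non-inferiority by the lower confidence limit in both the ITT and PP sets. A margin chosen now would be post hoc.

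The cost is a few sentences and one labelled interval, with no new data. The stated aim becomes slightly less ambitious. An unadjusted interval will sometimes disagree with the gated test (about 8% to 18% of trials in the scenarios of step 5); the label discloses this but does not remove it.

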## 3. Objectives

**Primary Objective.** Compare post-intervention clinical skill performance between arms using OSCE total scores.

**Secondary Objectives.** Compare reflection skills between arms immediately post-intervention; evaluate retention of clinical skills at follow-up OSCE; explore relationships between outcomes and exposure to peer support.

## 4. Endpoints

Primary Endpoint. OSCE total score immediately post-intervention (points; higher scores indicate better performance).

Secondary Endpoints. (i) Reflection skills total score immediately post-intervention (points; higher is better); (ii) Follow-up OSCE total score at a predefined interval to assess retention.

## 5. Trial Design

Individually randomized, parallel assignment with three arms. Participants are assigned in approximately equal numbers to the digital, face-to-face, or standard training arms. Interventions occur within routine clinical skills teaching sessions. No masking is used.

## 6. Study Setting

University-based Clinical Skills Laboratory and associated teaching rooms in Türkiye.

## 7. Eligibility Criteria

### Inclusion Criteria

- Enrolled medical students [specify year(s)].
- Age  $\geq 18$  and able to provide informed consent.
- Sufficient proficiency in the language of instruction.
- Access to the digital platform (for allocation to the digital arm).
- Availability for post-intervention and follow-up assessments.

### Exclusion Criteria

- Prior formal certification or extensive training in the targeted clinical skills.
- Inability to attend scheduled peer-support sessions (digital or face-to-face).
- Conditions preventing participation in OSCE/assessment procedures.

## 8. Interventions

Digital Interactive Peer Support (Behavioral). Structured peer learning via an online platform (modules, quizzes, discussion forums, and peer feedback).

Face-to-Face Peer Support (Behavioral). Structured in-person peer sessions with guided practice, observation, and formative feedback.

Standard Training (Control; Behavioral). Usual curriculum-based clinical skills training without additional structured peer support.

## 9. Procedures and Schedule

Following consent and baseline administrative checks, students receive instruction according to allocation. Outcome assessments include an immediate post-intervention OSCE and a validated reflection skills questionnaire. A follow-up OSCE is administered at a predefined interval (e.g., 8-12 weeks) to assess retention. Assessors use standardized checklists and instructions. No

investigational products are used.

## **10. Data Management and Confidentiality**

Data are recorded using de-identified codes and stored on secure institutional systems. Only authorized personnel have access to identifiable information. Aggregated results may be disseminated in publications without personal identifiers.

## **11. Ethics and Oversight**

The study was reviewed by an institutional ethics committee. Participation is voluntary, and students may withdraw at any time without academic penalty. The study involves minimal risk educational procedures. A Data Monitoring Committee is not planned for this low-risk trial.

# Statistical Analysis Plan (SAP)

This SAP prespecifies analysis populations, endpoints, statistical tests, missing data handling, and multiplicity control. Analyses will be conducted using a two-sided significance level of 0.05.

## 12. Analysis Populations

Intent-to-Treat (ITT): All randomized students with at least one post-intervention assessment.

Per-Protocol (PP): Subset without major protocol deviations.

## 13. Descriptive Statistics

Continuous variables will be summarized with mean, standard deviation, median, minimum, and maximum; categorical variables with counts and percentages.

## 14. Primary Endpoint Analysis

Between-arm comparison of immediate post-intervention OSCE total scores: if assumptions are met, one-way ANOVA; otherwise, Kruskal-Wallis test. If the omnibus test is significant, perform pairwise comparisons with multiplicity adjustment (e.g., Bonferroni or Holm).

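### With only three arms, does Bonferroni or Holm after a significant omnibus test waste power that the plan should recover?

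*Combined protocol and SAP*

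**What the plan says.** Section 5 sets the design: "Individually randomized, parallel assignment with three arms". The SAP's opening paragraph fixes the error level: "Analyses will be conducted using a two-sided significance level of 0.05".

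Section 14 picks the omnibus test from the data: "if assumptions are met, one-way ANOVA; otherwise, Kruskal-Wallis test". It then gates the pairs: "If the omnibus test is significant, perform pairwise comparisons with multiplicity adjustment (e.g., Bonferroni or Holm"). Section 18 repeats the rule and gives its purpose: "p-values will be adjusted (e.g., Bonferroni/Holm) to control the family-wise error rate". It names neither the final choice between the two adjustments nor the pairwise test.

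Section 15 extends the approach to reflection ("Reflection skills total score will be analyzed analogously to the primary endpoint") and describes retention as "comparing follow-up OSCE total scores between arms at the predefined time point using ANOVA or Kruskal-Wallis as appropriate", with no pairwise step of its own.

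The questions in Section 2 are pairwise: digital against face-to-face, and "whether either approach improves clinical skill performance compared with standard training".

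**The concern.** The answers this trial wants come from pairs of arms, and about 33 students per arm leaves limited power for each pair. A pair must pass two hurdles: the omnibus test and then an adjusted threshold. With three arms the second hurdle is not needed for family-wise error control, so it looks like power given away.

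The switch to Kruskal-Wallis adds a second worry. It depends on the data and changes the hypothesis. If skew and unequal spread occur together, a significant rank test may reflect shape or spread and not a difference in mean score.

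The apparent remedy is one package: Welch's ANOVA at 0.05 and, if it is significant, three Welch t-tests each at 0.05, with Kruskal-Wallis as a sensitivity analysis.

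**Working it through.** **Inputs.** Two-sided alpha 0.05 (SAP opening). Three arms (Section 5). About 100 students in a ratio near 1:1:1 (Section 1), so 100/3 ≈ 33 per arm. The plan has no power calculation to reproduce. Effect sizes, SDs, score shapes, the switching rule and the pairwise tests below are assumptions.

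**Step 1: is the adjustment needed?** If any two of the three pairwise nulls are true, all three means are equal. Three cases remain:

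- All equal: an error requires the omnibus test to reject, probability at most 0.05.
- Exactly one equal pair: an error requires that pair's test to reject, probability at most 0.05.
- None equal: no false rejection is possible.

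So a valid omnibus test followed by valid unadjusted pairs keeps the family-wise rate at 0.05. The gate is essential: three independent ungated tests would give 1 − 0.95³ = 14.3%.

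**Step 2: how conservative is the plan?** In simulation with normal scores and equal SDs, ANOVA plus Holm or Bonferroni has a family-wise error of 4.1% when all arms are equal. With one arm different, the null pair is falsely rejected in 1.6–1.8% of trials (Bonferroni) or 2.6–4.2% (Holm), reaching 5.0% only at very large effects.

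As a guide to cost, one ungated comparison has power of about Φ(d√(n/2) − z). With d = 0.7 SD and n = 33, d√(n/2) = 2.84. Power is Φ(2.84 − 1.96) = 81.2% at 0.05 and Φ(2.84 − 2.39) = 67.3% at 0.05/3, a gap of 13.9 points. The gate narrows this: with one arm 0.7 SD away, the Welch package has 75.1% per true pair against 65.6% for Bonferroni (9.5 points) and 68.8% for Holm (6.3 points).

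**Step 3: power with normal scores, equal SDs, ANOVA branch.** Both peer arms lie d SD above control; 100,000 simulated trials per cell. Cells show d = 0.4 / 0.6 / 0.8.

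| | Bonferroni | Holm | Welch package |
|---|---|---|---|
| Per true pair, % | 21.1 / 50.1 / 79.0 | 22.7 / 53.1 / 81.9 | 27.4 / 59.8 / 86.6 |
| At least one, % | 32.5 / 66.1 / 90.3 | 32.6 / 66.2 / 90.3 | 35.3 / 68.9 / 91.7 |
| Both, % | 9.7 / 34.0 / 67.6 | 12.8 / 40.0 / 73.5 | 19.4 / 50.6 / 81.5 |

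Over Holm this gains 4.7 / 6.7 / 4.7 points per pair and 2.7 / 2.7 / 1.4 for at least one. With one arm 0.9 SD away the gains are about 3 and 0.7.

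**Step 4: the whole plan, including a switch.** Assumed switch: Shapiro-Wilk on residuals or Brown-Forsythe below 0.05 leads to Kruskal-Wallis and rank-sum pairs. Both peer arms lie 0.6 SD above control with equal SDs; 20,000 trials per cell. Skewed scores are negated gamma.

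| Skewness | Sent to Kruskal-Wallis | Per pair: plan with Holm → Welch | Change | At least one: plan with Holm → Welch | Change |
|---|---|---|---|---|---|
| 0 | 9% | 53.4 → 60.4 | +7.0 | 66.4 → 69.2 | +2.8 |
| −0.7 | 70% | 54.5 → 60.1 | +5.6 | 68.5 → 70.8 | +2.3 |
| −1.0 | 94% | 59.0 → 61.2 | +2.2 | 73.7 → 72.6 | −1.1 |
| −1.4 | 100% | 67.8 → 61.0 | −6.8 | 82.0 → 73.0 | −9.0 |

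With normal scores and SDs 1/1/1.3, the gain is about 4 points per pair and about 0 for at least one difference.

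**Step 5: where the gain comes from.** In a separate run at 0.6 SD with normal scores and equal SDs, the plan with Holm gives 51.9% per pair, the plan's own tests unadjusted 59.8%, and the Welch package 59.2%. Dropping the adjustment contributes 59.8 − 51.9 = +7.9; Welch contributes 59.2 − 59.8 = −0.6. At skewness −1.4 a further run gives 68%, 76% and 61%: the loss comes from replacing Kruskal-Wallis. (Levels differ by a point or so between runs.)

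**Step 6: error rates with equal means and unequal spread.** For skewness 0 / −0.7 / −1.0 / −1.4:

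| SDs | Plan omnibus, % | Plan with Holm, family-wise, % | Welch package, % |
|---|---|---|---|
| 0.6/1.0/1.5 | 5.6 / 8.1 / 10.1 / 17.1 | 4.0 / 6.0 / 7.8 / 13.4 | 4.8 / 5.2 / 5.2 / 5.4 |
| 0.8/1.0/1.2 | 5.3 / 5.8 / 6.3 / 8.1 | 5.0 at skewness −1.0 | not tabulated |

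The large excess needs marked skew together with a 1.5/0.6 = 2.5-fold SD ratio. Here the adjustment also does useful work, bringing 17.1% down to 13.4% and 6.3% down to 5.0%. Leaving the plan's own tests unadjusted under skew with unequal spread gave 8.4% in one run and about 16% in the assumed worst case.

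**The case for a change.** The case for changing is serious. The closure argument is exact, the questions are pairwise, and the largest gain falls on showing that both peer formats beat control: 6.6, 10.6 and 8.0 points over Holm in Step 3 (for example 50.6 − 40.0 = 10.6). A fixed Welch test would also remove a data-driven choice and hold its error rate near 5% under unequal spread. The cost is some wording in Sections 14, 15 and 18.

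What stands is that the rule is conservative, and before data collection a statistician could reasonably have chosen the closed test. The following count against acting on it now.

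- **Target.** The robustness argument assumes the mean is the quantity of interest. Sections 3 and 4 compare total scores without naming a mean, and Section 13 summarises both mean and median. Where Kruskal-Wallis rejects too often for equal means, the score distributions do differ.
- **Two separate changes.** The power comes from dropping the adjustment and the robustness from Welch. The first without the second is unsafe under unequal spread; together, the power effect changes sign with score shape.
- **Timing.** Section 1 describes a completed trial registered retrospectively. Unless outcomes were demonstrably unseen, a looser pairwise rule could only be reported beside the planned one, as a deviation under Section 20.
- **Reporting.** Unadjusted gated tests have no matching simultaneous confidence intervals.

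Leaving Bonferroni or Holm open is a gap that analysts can fill sensibly. Holm never rejects less than Bonferroni under the same error control, and in Step 3 they differ by 1.6 to 3.0 points per pair.

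**Conclusion.** The concern is right that the adjustment exceeds what three arms require, but it does not call for a change. Sections 14 and 18 aim at family-wise error control, and the named methods deliver it when the component tests are valid.

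Against Holm, the alternative package would change power per true pair by about +7 points (normal, equal SDs), +4 (normal, SDs 1/1/1.3) or −7 (skewness −1.4, equal SDs), all at 0.6 SD. For at least one difference the corresponding changes are about +3, 0 and −9. More extreme skew makes the loss larger. The error-rate benefit is large only under marked skew combined with a 2.5-fold SD ratio; at SDs 0.8/1.0/1.2 and skewness −1.0 the plan with Holm holds 5.0%.

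These results assume 33 per arm, the stated effect sizes and shapes, and a switching rule that the SAP does not specify. Nothing in the documents shows which score shape applies. With an uncertain gain and a trial already completed, keeping the conservative planned analysis is a fair trade-off. The non-inferiority question in Section 2 is a separate matter that this point does not touch.

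### Arm contrasts are made only after a significant omnibus test and only as adjusted p-values; no between-arm difference with a confidence interval is planned for any endpoint

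*Combined protocol and SAP*

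**What the plan says.** Section 2 sets out the comparisons of interest: digital against face-to-face peer support, and "whether either approach improves clinical skill performance compared with standard training". Each of these concerns a named pair of arms.

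For the primary endpoint, Section 14 prescribes "if assumptions are met, one-way ANOVA; otherwise, Kruskal-Wallis test", and then "If the omnibus test is significant, perform pairwise comparisons with multiplicity adjustment", with Bonferroni or Holm given as examples. Section 18 repeats the condition and describes the output as adjusted p-values. Section 15 treats reflection in the same way as the primary endpoint. For retention it names only the three-arm test and mentions no pairwise step.

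Section 13 is not conditional on any test: "Continuous variables will be summarized with mean, standard deviation, median, minimum, and maximum". It names neither a difference between arms nor an interval. Section 16 allows optional exploratory adjusted models and specifies no estimate or interval from them.

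**The concern.** A three-arm omnibus test asks whether any arm differs from any other. The stated question is how far each peer arm differs from standard training, and how far the two peer arms differ from each other. Under the plan those contrasts appear only if the omnibus test succeeds, and then as p-values without a planned magnitude or precision.

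Two things are at stake. After a non-significant omnibus result, the planned output is a set of summaries and one p-value, which cannot separate absence of a useful effect from too little precision to tell. After a significant result, the contrasts that reach the report have been selected for being large, so they overstate the true effect on average.

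**Working it through.** **Inputs from the documents.** Total enrolment: "About 100 participants (retrospective registration of a completed trial"). Allocation: "Approximately 1:1:1; no masking". Level: "Analyses will be conducted using a two-sided significance level of 0.05". I take 33 per arm (3 × 33 = 99).

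**Inputs that are assumptions.** The documents state no effect size, OSCE standard deviation, power or dropout rate. Effects are therefore in SD units over a range from 0.3 to 0.8. There is no figure in the plan to reproduce.

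**How often the gate closes.** The power of one-way ANOVA comes from the noncentral F distribution with 2 and 96 degrees of freedom and noncentrality λ = Σ n(μᵢ − μ̄)²/SD².

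- Both peer arms better by d: the means are d, d, 0 and μ̄ = 2d/3. The squared deviations sum to d²(1/9 + 1/9 + 4/9) = 2d²/3, so λ = 33 × 2d²/3 = 22d².
- Second peer arm with half the effect: the means are d, d/2, 0 and μ̄ = d/2, so λ = 33 × d²/2 = 16.5d².

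| Assumed pattern | λ | Omnibus test not significant |
|---|---|---|
| both 0.3 SD | 1.98 | 78% |
| both 0.5 SD | 5.50 | 47% (power 53.1%) |
| both 0.6 SD | 7.92 | 30% (power 69.8%) |
| both 0.8 SD | 14.08 | 8% |
| 0.5 and 0.25 SD | 4.125 | 58% |

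If only one peer arm is better by 0.5 SD, λ is again 5.50 and the share is the same 47%. At 0.5 SD in both arms, using 33/33/34 gives 46%, 30 per arm (10% loss) gives 51%, and Kruskal-Wallis on simulated normal data gives about 48%.

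**Precision of one contrast.** With the pooled ANOVA variance, the half-width is t × SD × √(2/33), and √(2/33) = 0.246.

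- Unadjusted 95%: 1.985 × 0.246 = 0.49 SD.
- Bonferroni for three pairs: 2.437 × 0.246 = 0.60 SD.

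An observed difference of zero would thus still be compatible with a benefit of 0.49 SD on the unadjusted interval.

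**Selection by the gate.** In 40,000 simulated trials with a true 0.5 SD in both peer arms, the mean digital-versus-standard difference was about 0.65 SD when the omnibus test was significant and about 0.33 SD when it was not. Contrasts shown only after significance are inflated by 0.65/0.50 − 1 = 30%.

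**Which interval to add.** In the same set-up, at least one unadjusted 95% interval excludes zero in about 34% of the non-significant trials at 0.5 SD. With no true effect, about 7% of all trials combine a non-significant omnibus test with such an interval. For Bonferroni intervals on the pooled variance, the corresponding shares of non-significant trials are about 1% and 0.2%.

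**The case against.** The strongest reply is that the effect could still be recovered. Section 13 plans means and SDs without any gate, so if they are tabulated by arm, a reader can subtract them and, with arm sizes, build an interval. This stands against a stronger reading that a reader might infer, namely that after a non-significant omnibus test the study would report no estimate at all. The documents do not support that reading. What is missing is a planned contrast with an interval, and a reader's reconstruction does not supply one.

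Second, the 47% is not a property of the plan. It follows from an assumed 0.5 SD, and the share falls to 8% at 0.8 SD. It also measures only how often the formal contrasts are withheld. The missing interval is a separate gap, present whatever the omnibus result. Both points stand.

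Third, nothing in the documents says that a null omnibus result will be presented as evidence that peer support does not work. That is a risk of interpretation and not a stated intention.

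Fourth, the calculation describes the primary endpoint. Retention has no pairwise step in Section 15, and available cases at follow-up may be fewer than 33 per arm.

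Last, reporting intervals without a gate is not free. Unadjusted ones would often appear to contradict a non-significant omnibus test, as the 34% shows. This argues for adjusted intervals and does not argue against reporting estimates.

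**Conclusion.** The concern holds as a gap in estimation. The contrasts that Section 2 asks about are conditional on the omnibus test and planned only as adjusted p-values, and no endpoint has a planned between-arm difference with an interval. With about 33 per arm, normal data and equal benefit in both peer arms, the formal contrasts would be withheld in about 78% of trials at 0.3 SD, 47% at 0.5 SD, 30% at 0.6 SD and 8% at 0.8 SD. At 0.5 SD the share is about 58% if the second arm has half the effect. The case is therefore strong for small and moderate effects and weak for large ones.

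A reader should not infer that the planned tests are invalid: the gate and the adjustment may stand as rules for claiming significance. The non-inferiority wording in Section 2 would need a margin as well as an interval, which is a separate matter. The change should be made, but the trial's tests do not depend on it.

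**What to change.** Keep the omnibus gate for claims of significance and add to Sections 14 and 15:

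> Whatever the omnibus result, the three pairwise differences will be reported for each endpoint with Bonferroni-adjusted 95% confidence intervals: mean differences in points, or Hodges-Lehmann shifts when Kruskal-Wallis is used. Unadjusted intervals, if shown, are descriptive and support no claim of significance. A non-significant result will be interpreted from the interval and not as evidence of no effect.

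On the ANOVA branch, form the intervals from the pooled variance. In Sections 14 and 18, choose Bonferroni for the pairwise p-values as well, because Holm p-values can disagree with Bonferroni intervals.

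The Synopsis describes a completed trial, so this cannot be presented as prospective. Document it as a labelled addition in the results submission, which Section 20 already names as the place for deviations from the plan.

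The cost is one extra table per endpoint and half-widths of about 0.60 SD instead of 0.49 SD. No new data are needed. With the gate kept for claims, the error rate of the omnibus test does not change; choosing Bonferroni over Holm gives up a little pairwise power.
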